4.1 Confirmation of Patient Eligibility

Confirm patient eligibility by collecting the information listed below and scanning and emailing it to the research coordinator listed in the *Siteman Cancer Center Clinical Trials Core Protocol Procedures for Secondary Sites* packet at least two business days prior to registering patient:

1. Your name and contact information (telephone number, fax number, and email address)
2. Your site PI's name, the registering MD's name, and your institution name
3. Patient's race, sex, and DOB
4. Three letters (or two letters and a dash) for the patient's initials
5. Currently approved protocol version date
6. Copy of signed consent form (patient name may be blacked out)
7. Planned date of enrollment
8. Completed eligibility checklist, signed and dated by a member of the study team
9. Copy of appropriate source documentation confirming patient eligibility

4.2 Patient Registration in the Siteman Cancer Center OnCore Database

Registrations may be submitted Monday through Friday between 8am and 5pm CT. Urgent late afternoon or early morning enrollments should be planned in advance and coordinated with the Washington University research coordinator. Registration will be confirmed by the research coordinator or his/her delegate by email within two business days. Verification of eligibility and registration should be kept in the patient chart.

All patients at all sites must be registered through the Siteman Cancer Center OnCore database at Washington University.

4.3 Assignment of UPN

Each patient will be identified with a unique patient number (UPN) for this study. Patients will also be identified by first, middle, and last initials. If the patient has no middle initial, a dash will be used on the case report forms (CRFs). All data will be recorded with this identification number on the appropriate CRFs. UPN will be formatted as Site No. (XXX) – Patient No. (XXX). Site No. will be assigned by the Siteman Cancer Center and is site-specific; patient no. will be assigned by the Siteman Cancer Center and is patient-specific.

4.4 Screen Failures

Screen failures are defined as participants who consent to participate in the clinical trial but are not subsequently entered in the study (i.e. who do not subsequently undergo ctDNA testing). A minimal set of screen failure information is required to ensure transparent reporting of screen failure participants, to meet the Consolidated Standards of Reporting Trials (CONSORT) publishing requirements and to respond to queries from regulatory authorities. Minimal information includes demography, screen failure details, eligibility criteria, and any serious adverse event (if applicable).

4.5 Measures to Minimize Bias: Randomization

After enrollment to stage 1, patients who are determined to be ctDNA positive will be randomized to receive either atezolizumab and tiragolumab (treatment group) or atezolizumab monotherapy (reference group) on a 1:1 basis. The study will use a simple

randomization method. This method is equivalent to tossing a coin (where the probability of a head is 0.5) to determine treatment assignment (i.e., heads - atezolizumab and tiragolumab, tails – atezolizumab). Using the computer, a sequence of random numbers will be generated which are uniformly distributed between 0 and 1 and independent of each other. For the i-th patient entering the trial, if the i-th random number ≤ 0.5 , a combined treatment of atezolizumab and tiragolumab will be assigned; if the i-th random number > 0.5 then atezolizumab monotherapy will be assigned.

If it is determined (after analysis of stage 1) that enrollment will continue to stage 2, randomization will discontinue. All stage 2 patients will receive atezolizumab + tiragolumab.

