| Study Population: | During stage 1 of this study, 18 patients with stage II melanoma who have undergone complete resection and who have tested positive for ctDNA will be enrolled in each arm (atezolizumab + tiragolumab (treatment) vs. atezolizumab monotherapy (reference)) for a total of 36 patients randomized. If at least 3 patients in the atezolizumab + tiragolumab arm are shown to be ctDNA negative at C3D1, stage 2 of the study will begin enrollment. Stage 2 consists of 25 patients all enrolled to the atezolizumab + tiragolumab arm (no randomization and no atezolizumab monotherapy arm). With an anticipated ctDNA positive rate of 25%, a total of approximately 144 patients will need to be consented for ctDNA testing in stage 1 and 100 in stage 2. |
| Phase: | II |
| Description of Sites / Facilities Enrolling: | This study will be open at the Siteman Cancer Center at Washington University School of Medicine as well as other cancer centers in the United States. |
| Description of Study Intervention: | 
Patients who test positive for ctDNA will be randomized on a 1:1 basis during stage 1 to either treatment with atezolizumab and tiragolumab or treatment with atezolizumab alone. If, after the completion of stage 1, it is determined that enrollment will continue in stage 2, patients will not be randomized and all will receive treatment with atezolizumab and tiragolumab.
 
Atezolizumab is given as an IV infusion at a dose of 1680 mg every 4 weeks and tiragolumab is given as an IV infusion at a dose of 840 mg every 4 weeks.
 |
| Study Duration: | Study duration is anticipated to be 84 months (24 months for accrual + 12 months for treatment + 36 months for follow-up + 12 months for data analysis). Primary analysis will take place after all patients have completed adjuvant therapy. Additionally, an interim analysis will occur after 18 patients have been accrued to the treatment arm (atezolizumab + tiragolumab). |
| Participant Duration: | Forty-eight months (12 months for treatment + 36 months for follow-up) |

SCHEMA

SCHEDULE OF ACTIVITIES

Cycles are 28 days in duration. Step 2 screening may take place up to 28 days prior to C1D1 except where noted. Safety assessments may take place +/- 3 days from time point.

| | Step 1 Screening | Step 2 Screening | D1 of each cycle | Q12W ¹ | EOT | F/U ² |
|---|------------------|------------------|--|-------------------|-----------------|------------------|
| Screening consent | X | | | | | |

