5.3 Definitions of Evaluability

In order to be evaluable for the primary objective (ctDNA negativity at C3D1), a patient must have blood drawn to assess ctDNA at that time point. Patients in Stage 1 who discontinue treatment prior to C3D1 will be replaced; patients in Stage 2 who discontinue treatment prior to C3D1 will not be replaced.

All patients who receive any study treatment are evaluable for toxicity. Patients are evaluated from first receiving study treatment until a 90-day follow up after the conclusion of treatment or death.

All patients are evaluable for disease response unless they discontinue participation prior to having any disease assessment.

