14.0 STATISTICAL CONSIDERATIONS

14.1 Study Design

This is an open-label, multi-center, Simon two-stage phase II study consisting of random allocation of a portion of patients to a small reference arm to offer some protection against the uncertainties and potential biases of a one-armed study while retaining some of the statistical efficiency. The reference arm is not a control group in the traditional sense and there will not be a formal efficacy comparison between the treatment and reference groups (Herson and Carter, 1986; Rubinstein, et. al., 2009).

The purpose of this study is to evaluate the efficacy and safety of atezolizumab and tiragolumab in stage II melanoma patients who had undergone complete resection and been tested positive for circulating tumor DNA (ctDNA). In this study, the treatment arm (i.e., atezolizumab and tiragolumab) will not be compared with the reference arm (i.e., atezolizumab only); it will be analyzed against historical control as a one-armed study. The reference arm is intended to only act as a check on the similarity of the current patients to the historical control for a descriptive estimation of ctDNA clearance.

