14.5 Sample Size Determination

Under Simon's two-stage optimal design (Simon, 1989), with one-sided alpha = 0.05 and power = 0.8, assuming using atezolizumab and tiragolumab will have a ctDNA clearance rate of 25% and a null rate is 10%, in stage 1, 18 patients will be accrued for the treatment arm (atezolizumab + tiragolumab). If 3 or more patients are observed to be ctDNA-negative at C3D1 for the treatment arm, we will continue the treatment of atezolizumab and tiragolumab to stage 2 with an additional 25 patients being accrued. Otherwise the study will be stopped. If 8 or more ctDNA clearances are observed at the study completion, the combination of atezolizumab and tiragolumab will be considered promising for ctDNA-positive stage II melanoma patients.

Randomization will only happen in the stage 1. In total, 36 patients (18 per arm) will be randomly assigned in a 1:1 ratio to the treatment group (atezolizumab and tiragolumab) or reference group (atezolizumab monotherapy). There is no randomization in stage 2. Stage 2 is single-arm (i.e., the treatment arm only), with a sample size of 25.

According to PI's personal communication with the Natera team, we assume the ctDNA positive rate will be 25%. In stage 1, it is expected that up to 144 patients will be screened in order to randomize 36 patients (18 to each arm). If we continue the study to stage 2 with the treatment arm only, an additional 100 patients will be screened (in order to enroll 25 patients). In total, we expect to accrue 244 patients for ctDNA testing with 61 patients going on to treatment.

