14.6 Study Population

If the study stops after stage 1, we will screen 144 melanoma patients who had undergone complete resection. Among them, 18 ctDNA-positive patients being treated with the combination of atezolizumab and tiragolumab will be compared to a historical control and 18 ctDNA-positive patients on atezolizumab monotherapy will be analyzed as a descriptive comparison.

If we continue the study after stage 1, the study will screen 244 patients in total. Among them, 43 ctDNA-positive patients being treated with the combination of atezolizumab and

tiragolumab will be compared to a historical control and 18 ctDNA-positive patients on atezolizumab monotherapy will be analyzed as a descriptive comparison.

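### The coin-toss randomization in 4.5 does not deliver the stated 18-per-arm stage 1 allocation, and no rule says how patients are assigned once one arm reaches 18

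*Combined protocol and SAP*

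**What the plan says.** Section 4.5 specifies simple randomization. Each patient's uniform random number is compared with 0.5, independently of all others, and the text adds "This method is equivalent to tossing a coin (where the probability of a head is 0.5) to determine treatment assignment". It names no block, cap or other restriction.

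Other sections treat the arm sizes as fixed:

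- Protocol Summary, Study Population: 18 patients "will be enrolled in each arm (atezolizumab + tiragolumab (treatment) vs. atezolizumab monotherapy (reference)) for a total of 36 patients randomized".
- Section 14.5: "In total, 36 patients (18 per arm) will be randomly assigned in a 1:1 ratio to the treatment group".
- Section 14.6: "18 ctDNA-positive patients on atezolizumab monotherapy will be analyzed as a descriptive comparison".

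Three statements bear on when stage 1 allocation ends:

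- Protocol Summary, Study Duration: "an interim analysis will occur after 18 patients have been accrued to the treatment arm".
- Section 4.5: "If it is determined (after analysis of stage 1) that enrollment will continue to stage 2, randomization will discontinue".
- Section 14.5 confines randomization to stage 1. It has 18 accrued to the combination in stage 1 and 25 more in stage 2.

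On replacement, 5.3 says "Patients in Stage 1 who discontinue treatment prior to C3D1 will be replaced". It does not say to which arm, or by what mechanism. On the purpose of the second arm, 14.1 says "The reference arm is intended to only act as a check on the similarity of the current patients to the historical control".

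**The concern.** A 1:1 ratio is met in expectation by a coin toss, but the stated counts usually are not. Unless the split happens to be 18:18 at patient 36, one arm is full while the other is short, and the team has to decide in an open-label trial what to do next. The interim trigger says when the analysis occurs, not how patients are allocated up to that point.

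At least four conventions are possible: stop at 18 on the combination, cap each arm at 18 and send later patients to the open arm, continue until both arms have at least 18, or stop at 36 whatever the split. They differ in reference-arm size, in total randomized and screened, in concealment, and (for two of them) in whether the Simon cutoffs still apply to the number for which they were derived.

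Replacement raises the same problem. A fresh toss refills the arm that lost a patient only half the time.

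**Working it through.** **Inputs.** Assignment probability 0.5, independent (4.5). Stage 1 total 36, 18 per arm (Summary, 14.5). Null and target clearance rates 10% and 25%; continue if at least 3 of 18; promising if at least 8 of 43; one-sided alpha 0.05, power 0.80 (14.4, 14.5). ctDNA-positive rate 25% (14.5).

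**1. The plan's own design.** With X1 ~ Bin(18, p) and X2 ~ Bin(25, p), P(promising) = sum over x from 3 to 18 of P(X1 = x) × P(X2 ≥ 8 − x). At p = 0.10 this is 0.0480; at p = 0.25 it is 0.8003. The stated design is reproduced.

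**2. Chance of the stated split.** C(36,18) × 0.5^36 = 9,075,135,300 / 68,719,476,736 = 0.132. The combination arm has 16 to 20 patients in 59% of sequences, and the mean absolute difference between arms is 4.8.

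**3. Stop at 18 on the combination.** Step 1 is unchanged: alpha 0.048, power 0.800. The reference-arm size is negative binomial(18, 0.5): median 17, middle half 14 to 22, 95% range 8 to 31. Total randomized is then 18 + 8 = 26 to 18 + 31 = 49. Dividing by 0.25 gives about 104 to 196 screened, against 144 planned. For the similarity check, exact 95% intervals for an observed rate near the 10% historical rate are:

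| Reference arm | Observed | 95% CI |
|---|---|---|
| 8 | 1/8 | 0.3% to 52.7% |
| 18 | 2/18 | 1.4% to 34.7% |
| 31 | 3/31 | 2.0% to 25.8% |

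**4. Cap each arm at 18.** All stated counts are met and step 1 is unchanged. The first arm fills on average at patient 31.2, so 36 − 31.2 = 4.8, about 5 patients, are assigned with certainty to the open arm.

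**5. Continue until both arms have at least 18.** P(total = t) = 2 × C(t−1, 17) × 0.5^t for t ≥ 36. The mean total is 40.8 (95% range 36 to 51), or about 163 screened. The combination arm exceeds 18 in 43% of sequences. Testing only its first 18 keeps alpha 0.048. Applying the cutoffs to all its stage 1 patients, with 25 added, gives average alpha 0.070 and power 0.845.

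**6. Stop at 36 with the cutoffs unchanged.** Averaging the step 1 sum over n1 ~ Bin(36, 0.5) with 25 added gives alpha 0.0505 and power 0.782. In the tails, n1 = 14 gives power 0.641 and n1 = 22 gives alpha 0.081. A combination arm of 14 or fewer has probability 12%, as does one of 22 or more.

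**7. Predictability of lists that end at 18:18.** Suppose someone knows every earlier assignment and always guesses the arm that is behind. The expected number of correct guesses in a balanced block of 2m is m + 4^m / (2 × C(2m, m)) − 0.5. One shuffled list of 36 (m = 18) gives 21.29/36 = 59%. Blocks of 6, 8, 10 and 12 give (4.10 + 5.33 + 6.53 + 7.72)/36 = 23.68/36 = 66%. A coin toss gives 50%.

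**The case against.** The best defence is that no planned primary analysis needs an 18:18 split. Section 14.5 fixes 18 on the combination in stage 1 and then 25 more, and the Summary ties the interim to the same 18. Section 14.1 disclaims any formal efficacy comparison, and 14.7 labels all analyses exploratory, which covers its log-rank test between arms. Simple randomization is valid and is the least predictable method, which matters in an open-label multicentre trial. The screening spread in step 3 is also not due to the coin toss alone: with exactly 36 randomized, chance variation around 25% positivity already gives about 107 to 188.

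Most of this stands, and it limits the point. It rules out two stronger readings that a reader might infer. One is that the coin toss damages the type I error or power of the trial. Steps 5 and 6 show that this needs a stage 1 combination arm other than 18 with unchanged cutoffs, and 14.5 supports neither. The other is that randomization simply continues while C3D1 results mature, because 4.5 ends it only after the stage 1 analysis. That conflicts with 14.5, which restricts randomization to stage 1 and totals it at 36. The sentence in 4.5 can be read as saying only that stage 2 is not randomized.

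The defence does not supply the missing rule. Capping each arm at 18 fits every stated count, but it is written nowhere, and it gives up concealment for the last few patients.

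**Conclusion.** The point holds as a mismatch between method and stated numbers. The procedure in 4.5 gives the stage 1 allocation of the Summary, 14.5 and 14.6 in 13.2% of sequences at 36 patients, and no section governs the other 86.8%.

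Provided that the combination arm has 18 patients in stage 1, the Simon test is intact at alpha 0.048 and power 0.800. The consequence is then one of two things. If stage 1 closes at 18 on the combination, the reference-arm size is uncertain (95% range 8 to 31), and with it the numbers randomized and screened. At the lower end, the check against the historical control would tell very little. If each arm is capped at 18, about 5 late assignments are deterministic.

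The figures assume independent draws at 0.5, as 4.5 states, and leave replacements aside; the screening figures also assume 25% positivity. Severity is minor to moderate.

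**What to change.** - **4.5:** replace the coin toss with a central, concealed, restricted list that ends at exactly 18:18. One shuffled list of 18 + 18 is the less predictable choice (about 59% guessable by someone who knows all earlier assignments). Undisclosed blocks of varying size, such as 6, 8, 10 and 12 in random order, are an alternative (about 66%).
- **4.5 and 14.5:** state that stage 1 randomization closes at 18 per arm.
- **5.3:** state how a replacement is assigned, so that the arm that lost the patient is refilled through central assignment.

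The cost is a new list, a paragraph in 4.5 and a sentence each in 14.5 and 5.3. The downside is slightly more predictable assignment in an open-label trial, mainly near the end of the list. Refilling a given arm is also not a random assignment, and the 59% and 66% figures do not include that. Central assignment and several sites limit both.

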4.6 Screening and Enrollment Considerations

The screening and enrollment targets outlined below should be considered in order to maintain adequate momentum towards trial completion. If at any time a screening or enrollment milestone cannot be met, the sponsor may elect to employ additional screening enhancement strategies upon discussion with Genentech/Roche, and consider stopping the study altogether due to feasibility.

| | Screening Target | Sub-Site Participation | Enrollment Target |
|--------------------|---|----------------------------------|-------------------|
| 6-month milestone | 20% of Stage 1 patients screened (n>28) | 1 additional sub-site added | n>5 enrolled |
| 12-month milestone | 40% of Stage 1/II patients screened (n>97) | 1 additional sub-site added | n>19 enrolled |
| 18-month milestone | 60% of Stage 1/II patients screened (n>144) | 1 additional sub-site (optional) | n>29 enrolled |
| 24-month milestone | 80% of Stage I/II patients screened (n>195) | -- | n>39 enrolled |

5.0 TREATMENT PLAN

5.1 Study Intervention Description

Atezolizumab is a PD-L1 blocking antibody which is indicated for the treatment of:

- some adult patients with locally advanced or metastatic urothelial carcinoma
- adult patients with metastatic non-squamous non-small cell lung cancer with no EGFR or ALK genomic tumor aberrations (in combination with bevacizumab, paclitaxel, and carboplatin)
- adult patients with metastatic non-small cell lung cancer who have disease

- progression during or following platinum-containing chemotherapy
- adult patients with extensive-stage small cell lung cancer (in combination with carboplatin and etoposide)

Tiragolumab is a fully human IgG1/kappa mAb that binds TIGIT (T-cell Immunoreceptor with Immunoglobulin and Immunoreceptor Tyrosine-Based Inhibition Motif [ITIM] domains) and prevents its interaction with PVR (Poliovirus Receptor).

5.2 Study Intervention Administration

Consenting and eligible patients will undergo a blood draw to test for ctDNA 4 to 12 weeks after surgery. Twenty mL of blood will be drawn into 2 10-mL Streck tubes as described in Section 9.0.

During stage 1 of the study, patients who are ctDNA-positive will be randomized on a 1:1 basis either to receive atezolizumab + tiragolumab or atezolizumab alone. If, after analysis of stage 1 data, it is determined that enrollment will continue to stage 2, all patients will receive atezolizumab + tiragolumab.

Atezolizumab is given as an IV infusion every 4 weeks at a dose of 1680 mg over 60 minutes (+/- 15 minutes). If this rate of infusion is tolerated without an infusion-related reaction, subsequent infusions of atezolizumab may be given over 30 minutes (+/- 10 minutes). Otherwise, the rate of infusion remains 60 minutes (+/- 15 minutes). After the first infusion of atezolizumab, the patient begins a 60-minute observation period during which vital signs should be recorded at 30 (+/-10 minutes) after infusion. If the patient tolerated the first infusion well without infusion-associated adverse events, the observation period after the next and following infusions may be reduced to 30 minutes. If the patient experienced infusion-associated adverse events in the previous infusion, the observation period should be 60 minutes. If clinically indicated, vital signs should be recorded at 30 (+/- 10) minutes after the infusion of atezolizumab.

Tiragolumab is given as an IV infusion every 4 weeks at a dose of 840 mg over 60 minutes (+/- 15 minutes). If this rate of infusion is tolerated without an infusion-related reaction, subsequent infusions of tiragolumab may be given over 30 minutes (+/- 10 minutes). Otherwise, the rate of infusion remains 60 minutes (+/- 15 minutes). After the first infusion of tiragolumab, the patient begins a 60-minute observation period during which vital signs should be recorded at 30 (+/-10 minutes) after infusion. If the patient tolerated the first infusion well without infusion-associated adverse events, the observation period after the next and following infusions may be reduced to 30 minutes. If the patient experienced infusion-associated adverse events in the previous infusion, the observation period should be 60 minutes. If clinically indicated, vital signs should be recorded at 30 (+/- 10) minutes after the infusion of tiragolumab.

Treatment can continue for up to 13 cycles. For patients receiving both drugs, atezolizumab will be given first, followed by tiragolumab. If either study drug is delayed for a related toxicity, it is recommended that the other study drug is also delayed (if

applicable) since the safety profiles for atezolizumab and tiragolumab are similar.

All patients will receive CT scans every 12 weeks for the first two years after initiation of treatment, then every 24 weeks for the next year; frequency of scans will not be adjusted in the event of a treatment delay.

Administration of First and Subsequent Infusions of Atezolizumab and Tiragolumab

| Study drug | First Infusion | Subsequent Infusions |
|---|---|---|
| Atezolizumab infusion | 
 • No premedication is permitted prior to the atezolizumab infusion. • Vital signs (pulse rate, respiratory rate, blood pressure, and temperature) should be recorded within 60 minutes prior to the infusion. • Atezolizumab should be infused over 60 (\pm 15) minutes. • If clinically indicated, vital signs should be recorded every 15 (\pm 5) minutes during the infusion. | 
 • If the patient experienced an IRR with any previous infusion of atezolizumab, premedication with an antihistamine and/or antipyretic medication may be administered for subsequent doses at the discretion of the investigator. • Vital signs should be recorded within 60 minutes prior to the infusion. • Atezolizumab should be infused over 30 (\pm 10) minutes if the previous infusion was tolerated without an IRR or 60 (\pm 15) minutes if the patient experienced an IRR with the previous infusion. • If the patient experienced an IRR with the previous infusion, or if clinically indicated, vital signs should be recorded during the infusion. |
| Observation period after infusion of atezolizumab | 
 • After the infusion of atezolizumab, the patient begins a 60-minute observation period. • Vital signs should be recorded at 30 (\pm 10) minutes after the infusion of atezolizumab. • Patients will be informed about the possibility of delayed post-infusion symptoms and instructed to contact their study physician if they develop such symptoms. | 
 • If the patient tolerated the previous atezolizumab infusion well without infusion-associated adverse events, the observation period after the next and following infusions may be reduced to 30 minutes. • If the patient experienced infusion-associated adverse events in the previous infusion, the observation period should be 60 minutes. • If clinically indicated, vital signs should be recorded at 30 (\pm 10) minutes after the infusion of atezolizumab. |
| Infusion of tiragolumab | 
 • No premedication is permitted prior to the tiragolumab infusion. • Vital signs (pulse rate, respiratory rate, blood pressure, and temperature) should be recorded within 60 minutes prior to the infusion. | 
 • If the patient experienced an IRR during any previous infusion of tiragolumab, premedication with an antihistamine and/or antipyretic may be administered for subsequent doses, at the discretion of the investigator. • Vital signs should be recorded within 60 minutes prior to the tiragolumab infusion. |

| Study drug | First Infusion | Subsequent Infusions |
|--|--|---|
| | 
 • Tiragolumab should be infused over 60 (\pm 15) minutes. • Vital signs should be recorded every 15 (\pm 5) minutes during the infusion. | 
 • Tiragolumab should be infused over 30 (\pm 10) minutes if the previous infusion was tolerated without an infusion-related reaction, or 60 (\pm 15) minutes if the patient experienced an infusion-related reaction with the previous infusion. • Vital signs should be recorded during the infusion if clinically indicated. |
| Observation period after infusion of tiragolumab | 
 • After the infusion of tiragolumab, the patient begins a 60-minute observation period. • Vital signs should be recorded at 30 (\pm 10) minutes after the infusion of tiragolumab. • Patients will be informed about the possibility of delayed post-infusion symptoms and will be instructed to contact their study physician if they develop such symptoms. | 
 • If the patient tolerated the previous infusion of tiragolumab well without infusion-associated adverse events, the observation period may be reduced to 30 minutes. • If the patient experienced an infusion-associated adverse event in the previous infusion, the observation period should be 60 minutes. • If clinically indicated, vital signs should be recorded at 30 (\pm 10) minutes after the infusion of tiragolumab. • Patients will be informed about the possibility of delayed post-infusion symptoms and will be instructed to contact their study physician if they develop such symptoms. |

IRR = infusion-related reaction.

